APPENDIX B – DETAILED STUDY SCHEMA

SCREENING	
Up to 4 weeks prior	Screening
	
• Obtain informed consent• Review demographic parameters• Conduct a joint evaluation as per the SOC at hemophilia treatment center• Screen potential subjects by inclusion and exclusion criteria• Obtain medical and hemophilia history, document• Evaluate concomitant medications, check vital signs, height and weight• Conduct physical examination, check for clinical signs of thrombosis• Conduct testing for hematology and chemistry, coagulation assay, thrombogenicity markers, immunogenicity assays, and ECG• Adverse Events

CB2679d DLZ-201 VERSION 1.0

Part 1 – 14 days	
Day 1 Pre-IV Dose – 5 min	Part 1

• Evaluate concomitant medications, check vital signs, and weight• Conduct physical examination, check for clinical signs of thrombosis• Conduct testing for hematology and chemistry, coagulation assay, thrombogenicity markers, PK sampling, immunogenicity assays• Conduct study subject diary training• Diary entry of bleeding episodes, AEs, injection site assessment• Check for AEs	
Day 1 IV Dose Followed by SQ Dose; Day 2 to Day 14 SQ Dose	Part 1

• Day 1: Administer single IV 70 IU/kg loading dose of CB2679d• Day 1: 30 minutes later administer SQ 140 IU/kg dose of CB2679d• Day 2 to 14: Administer SQ 140 IU/kg dose of CB2679d	
Day 1 Post-Dose SQ Dose – (30 min and Hr 7); Day 2 Post-Dose SQ Dose – Hr 24	Part 1

• Evaluate concomitant medications and check vital signs• Conduct physical examination, check for clinical signs of thrombosis• Conduct testing for thrombogenicity markers, PK sampling• Diary entry of bleeding episodes, AEs, injection site assessment• Check for AEs	
Days 5, 8, 11 and 14 Pre Dose	Part 1

• Evaluate concomitant medications and check vital signs• Conduct physical examination, check for clinical signs of thrombosis• Day 8 and 14 only: Conduct testing for hematology and chemistry• Conduct testing for thrombogenicity markers, PK sampling• Day 8 only: Conduct testing for immunogenicity assays• Diary entry of bleeding episodes, AEs, injection site assessment• Check for AEs	

CB2679d DLZ-201 VERSION 1.0

Part 2 – 7 days	
Dose Hr 0 on Day 15, Day 17, Day 19, and Day 21	Part 2

Administer 280 IU/kg SQ dose of CB2679d (every second day)	
Day 15 Pre-Dose – 5 min	Part 2

Evaluate concomitant medications, and check vital signs and weightConduct physical examination, check for clinical signs of thrombosisConduct testing for thrombogenicity markers, PK sampling, and immunogenicity assaysDiary entry of bleeding episodes, AEs, injection site assessment, check for AEs	
Day 15 Post-Dose at Hour 7 [\pm 1 hour]; Day 16 Post-Dose at Hour 24 [\pm 1 hour]; Day 17 and Day 19 Pre-Dose - 5 min	Part 2

Evaluate concomitant medications and check vital signsConduct physical examination, check for clinical signs of thrombosisConduct testing for thrombogenicity markers, PK samplingDiary entry of bleeding episodes, AEs, injection site assessment, check for AEs	
Day 21 Pre-Dose - 5 min	Part 2

Evaluate concomitant medications, and check vital signs and weightConduct physical examination, check for clinical signs of thrombosisConduct testing for hematology and chemistry, thrombogenicity markers, PK samplingDiary entry of bleeding episodes, AEs, injection site assessment, check for AEs	

CB2679d DLZ-201 VERSION 1.0

Part 3 – 14 Days	
Dose Hr 0 on Day 23, Day 26, Day 29, and Day 32	Part 3

Administer 420 IU/kg SQ dose of CB2679d (every third day)	
Day 23 and Day 32 Pre-Dose – 5 min	Part 3

Evaluate concomitant medications and check vital signsConduct physical examination, check for clinical signs of thrombosisDay 23 only: Check weight and conduct testing for hematology and chemistryConduct testing for thrombogenicity markers, PK sampling, immunogenicity assaysDiary entry of bleeding episodes, AEs, injection site assessment, check for AEs	
Day 24 Post-Dose at Hour 24 [± 1 hr]; Day 26 and 29 Pre-Dose – 5 min	Part 3

Evaluate concomitant medications and check vital signsConduct physical examination, check for clinical signs of thrombosisConduct testing for thrombogenicity markers, PK samplingDiary entry of bleeding episodes, AEs, injection site assessment, check for AEs	
Day 32 Post-Dose at Hour 7 [± 1 hour]	Part 3

Dalcinonacog alfa_DLZ-201 VERSION 2.0, Amendment 1

DETAILED SUMMARY OF PROTOCOL CHANGES

Protocol Number: DLZ-201

Protocol Title: Phase 2b study to evaluate the pharmacokinetics, pharmacodynamics, efficacy and safety of a subcutaneous prophylaxis treatment regimen of CB2679d, in adult subjects with hemophilia B

	Version Number	Version Date
Current Approved Protocol	1.0	23 March 2018
Amended Protocol	2.0, Amendment 1	17 October 2018

Description of Changes:

Section	Update	Details
Title Page	Replacement	VERSION NUMBER: 1.0 With: VERSION NUMBER: 2.0, Amendment 1
Title Page	Replacement	Effective Date: 23 March 2018 With: Effective Date: 17 October 2018
Investigator Signature Page	Replacement	VERSION NUMBER: 1.0 With: VERSION NUMBER: 2.0, Amendment 1
Sponsor Signature Page	Replacement	Version Number: 1.0, dated 23 March 2018 With:

Dalcinonacog alfa_DLZ-201 VERSION 2.0, Amendment 1

Version Number: 2.0, Amendment 1		
Abbreviations	Updated	SQ With: SC
1.1 Synopsis: Study Population:	Updated	Five male subjects, aged 18 or older, with confirmed diagnosis of severe congenital hemophilia B (<2% FIX level). With: Six male subjects, aged 18 or older, with confirmed diagnosis of severe congenital hemophilia B (<2% FIX level).
1.1 Synopsis: Participant Duration:	Updated	The duration of treatment for each subject is approximately 6 weeks. With: The duration of treatment for each subject is approximately 4 weeks.
1.1 Synopsis: IV/SQSC Study Drug Administration and Assessments	Updated	Part 1; Weeks 1 and 2: The subject will receive an IV loading dose of 70 IU/kg followed 30 minutes later by a SQ dose of 140 IU/kg. Daily SQ doses of 140 IU/kg will be administered until Day 14 (14 total SQ doses). On day 1, PK, PD, and safety assessments will be done at pre-IV dose and repeated 30 minutes later prior to the SQ dose. Subsequent PK, PD and safety assessments will be performed 7 hours post-SQ dose on Day 1, Day 2 at hour 24 post-SQ dose and pre-dose on days 5, 8, 11 and 14. With: Treatment: Day 1 to Day 28: The subject will receive an IV loading dose of 50 IU/kg followed 35 ± 5 minutes later by a SC dose of 100 IU/kg. Daily SC doses of 100 IU/kg will be administered until Day 28 (28 total SC doses). On Day 1, PK, PD, and safety assessments will

Dalcinonacog alfa_DLZ-201 VERSION 2.0, Amendment 1

		be done at pre-IV dose and repeated 35 (± 5) minutes later prior to the SC dose. Subsequent PK, PD and safety assessments will be performed pre-dose on days 2, 3, 7, 14, 21 and 28 .
1.1 Synopsis: IV/SQSC Study Drug Administration and Assessments	Deletions	
Every Second Day SQ study drug administration
 
Part 2; Week 3: The subject will receive a SQ dose every second day of 280 IU/kg, starting on Day 15 until Day 21 (total of 4 SQ doses). On Day 15 only, PK, PD, and safety assessments will be done at pre-dose and repeated at hour 7. Subsequent PK, PD and safety assessments will be performed on Day 16 at hour 24 and pre-dose on days 17, 19 and 21.
 
Every Third Day SQ study drug administration
 
Part 3; Weeks 4 and 5: The subject will receive a SQ dose every third day of 420 IU/kg, starting on Day 23 until Day 32 (total of 4 SQ doses). On days 23 and 32 only, PK, PD, and safety assessments will be done at pre-dose and repeated at hour 7. Subsequent PK, PD, and safety assessments will be performed at Day 24 at hour 24 and pre-dose on days 26, and 29.

1.1 Synopsis: Washout Period	Updated	Days 33, 34, 35, 37, and 38 With: Days 29, 30, 31, 32, and 33
1.1 Synopsis: Measurements: and Throughout	Updated	CB2679d activity levels With: FIX activity levels
1.1 Synopsis: Measurements:	Added	Genotype testing will be performed at screening.
1.1 Synopsis: Measurements: Immunogenicity assays	Updated	Specimens for immunogenicity testing (antibody to CB2679d, wild-type FIX cross reactivity, and neutralizing activity) will be drawn at screening, on days 1, 8, 15, 23, 32, and end of study.

Dalcinonacog alfa_DLZ-201 VERSION 2.0, Amendment 1

		With: Specimens for immunogenicity testing (antibody to CB2679d, BeneFIX®, and neutralizing activity) will be drawn at screening, on days 7, 14, 21, 28, and end of study.
1.1 Synopsis: Measurements: Immunogenicity assays and Throughout	Updated	Wild-type FIX With: BeneFIX®
1.1 Synopsis: Number of planned subjects	Updated	5 With: 6
1.1 Synopsis: Exclusion Criteria:	Added	12. Factor IX gene mutation 128G>A.
1.1 Synopsis: Dosage and mode of administration:	Updated	Part 1: Weeks 1 and 2 (Days 1-14): IV loading dose of 70 IU/kg followed 30 minutes later with 140 IU/kg SQ administration daily x 14 (14 total doses). Part 2: Week 3 (Days 15, 17, 19 and 21): 280 IU/kg, SQ administration every second day (4 total doses). Part 3: Weeks 4 and 5 (Days 23, 26, 29, 32): 420 IU/kg SQ administration every third day (4 total doses) With: IV loading dose of 50 IU/kg, followed 35 ± 5 minutes later with 100 IU/kg SC administration, then daily SC administration until Day 28 (28 total SC doses).
1.1 Synopsis: Primary Endpoints	Updated	Number of subjects who achieve a steady-state FIX activity level above 12%, 30% and 50% with daily, every second day or every third day dosing. With:

Dalcinonacog alfa_DLZ-201 VERSION 2.0, Amendment 1

		Number of subjects who achieve a steady-state FIX activity level above 12% with daily dosing.
1.1 Synopsis: Secondary Endpoints	Deletion	Feasibility of using an adjusted-dose SQ prophylaxis treatment regimen clinically.
1.1 Synopsis: Primary Analysis Plan	Updated	The dose required to achieve steady-state levels >12%, >30% and >50% will be reported for daily, every second day or every third day dosing, including 95% confidence intervals. With: The dose required to achieve steady-state levels >12% will be reported for daily dosing, including 95% confidence intervals.
1.1 Synopsis: Rationale for Number of Subjects	Updated	5 subjects will provide guidance on dose required to achieve steady-state activity >12%, 30% or 50% and starting SQ dose for subsequent studies. With: 6 subjects will provide guidance on dose required to achieve steady-state activity >12% and starting SC dose for subsequent studies.
1.2 Schema	Updated	Figure 1. Schematic of Study Design
1.3 Schedule of Activities (SOA)	Updated and Deletions	Updated Table. Deleted Tables for Parts 2 and 3.
2.2.2 Experience with CB2679d in the Clinic	Updated and Addition	An intravenous loading dose has been added in this study to see if it eliminates these local adverse events as they are believed to be due to low FIX levels because of washout of prior treatment. With:

Dalcinonacog alfa_DLZ-201 VERSION 2.0, Amendment 1

		
An IV loading dose has been added to cohort 6 in this study to see if it eliminates injection site adverse events as they are believed to be due to low FIX levels because of washout of prior treatment (Figure 2).
 
ADDED:
 
The nadir activity after IV plus SC dosing was 20% in both subjects in cohort 6 and thereafter levels increased to >30%. It is clear that the IV loading dose increased the bioavailability of SC CB2679d by increasing the saturation of the extravascular compartment and resulted in greater activity levels than simple addition of SC to IV activity. Neutralizing antibodies developed in both subjects, (transiently in one subject). A root cause analysis determined that the most likely cause was a 3-month gap between dosing in cohort 5 and cohort 6 in these 2 participants (Figure 3).
 
FIGURE 2. CB2679D PHASE 1/2 OPEN LABEL STUDY DESIGN
 
FIGURE 3. CB2679D PHASE 1/2 STUDY: COHORT 5 & 6 FIX ACTIVITY RESULTS

4.1 Overall Design	Updated	
Each subject will participate for approximately 6-weeks of SQ CB2679d drug administrations:
 
Part 1; Weeks 1 and 2: Each participant will receive an IV loading dose of 70 IU/kg followed 35 ± 5 minutes later by a SQ dose of 140 IU/kg. Daily SQ doses of 140 IU/kg will be administered until Day 14 (14 total SQ doses). On day 1, PK, PD, and safety assessments will be done at pre-IV dose and repeated 30 minutes later prior to the SQ dose. Subsequent PK, PD and safety assessments will be performed 7 hours post-SQ dose on Day 1, Day 2 at hour 24 post-SQ dose and pre-dose on days 5, 8, 11 and 14.
 
With:

Dalcinonacog alfa_DLZ-201 VERSION 2.0, Amendment 1

		
Treatment: Day 1 to Day 28: Each participant will receive an IV loading dose of 50 IU/kg followed 35 ± 5 minutes later by a SC dose of 100 IU/kg. Daily SC doses of 100 IU/kg will be administered until Day 28 (28 total SC doses). On day 1, PK, PD, and safety assessments will be done at pre-IV dose and repeated 35 (± 5) minutes later prior to the SC dose. Subsequent PK, PD and safety assessments will be performed pre-dose on days 2, 3, 7, 14, 21 and 28.

4.1 Overall Design	Deletions	
Every Second Day SQ study drug administration
 
Part 2; Week 3: The subject will receive a SQ dose every second day of 280 IU/kg, starting on Day 15 until Day 21 (total of 4 SQ doses). On Day 15 only, PK, PD, and safety assessments will be done at pre-dose and repeated at hour 7. Subsequent PK, PD and safety assessments will be performed on Day 16 at hour 24 and pre-dose on days 17, 19 and 21.
 
Every Third Day SQ study drug administration
 
Part 3; Weeks 4 and 5: The subject will receive a SQ dose every third day of 420 IU/kg, starting on Day 23 until Day 32 (total of 4 SQ doses). On days 23 and 32 only, PK, PD, and safety assessments will be done at pre-dose and repeated at hour 7. Subsequent PK, PD, and safety assessments will be performed at Day 24 at hour 24 and pre-dose on days 26, and 29.

4.1 Overall Design: Washout Period	Updated	
Days 33, 34, 35, 37, and 38
 
With:
 
Days 29, 30, 31, 32, and 33

4.1 Overall Design: Measurements	Added	Genotype testing will be performed at screening.
4.1 Overall Design: Measurements	Updated	
Immunogenicity assays: Specimens for immunogenicity testing (antibody to CB2679d, wild-type FIX cross reactivity, and

Dalcinonacog alfa_DLZ-201 VERSION 2.0, Amendment 1

		
neutralizing activity) will be drawn at screening, pre-dose on days 1, 8, 15, 23, 32 and end of study.
 
With:
 
Immunogenicity assays: Specimens for immunogenicity testing (antibody to CB2679d, BeneFIX®, and neutralizing activity) will be drawn at screening, pre-dose on days 7, 14, 21, 28 and end of study.

4.6 End of Study Definition	Updated	
The duration of treatment for each subject is approximately 6 weeks.
 
With:
 
The duration of treatment for each subject is approximately 4 weeks (28 days).

5.2 Exclusion Criteria	Added	12. FIX mutation 128G>A.
6.1.2 Dosing and Administration	Updated	
CB2679d loading dose of 70 IU/kg IV, followed 30 minutes later with a 140 IU/kg, SQ administration daily x 14 (total 1 IV dose and 14 SQ doses); then a 280 IU/kg, SQ administration every second day, starting on Day 15 until Day 21 (total 4 SQ doses); then a 420 IU/kg SQ every third day, starting on Day 23 until Day 32 (total of 4 SQ doses).
 
With:
 
CB2679d loading dose of 50 IU/kg IV, followed 35 ± 5 minutes later with a 100 IU/kg, with SC administration daily until Day 28 (total 1 IV dose and 28 SC doses).

6.4 Study Intervention Compliance	Updated	
Reasonable efforts should be made to ensure that study drug administration is administered according to the schedule. However, if an unavoidable disruption of the administration occurs, and a dose is not administered on the assigned day then the subject should take the dose as soon as possible. In the event that the

Dalcinonacog alfa_DLZ-201 VERSION 2.0, Amendment 1

		
subject remembers more than 2 days late, then the subject must contact the research site for instructions on how to proceed.
 
With:
 
Reasonable efforts should be made to ensure that study drug administration is administered daily according to the schedule. However, if an unavoidable disruption of the administration occurs, and a dose is not administered on the assigned day then the subject should take the dose as soon as possible. In the event that the subject does not take study drug for more than 2 days, then the subject must contact the research site for instructions on how to proceed prior to administering a dose.

7.1 Participant Discontinuation/Withdrawal from Study	Updated	
Replacement of a subject occurs for the following reason:
 
If a subject does not complete at least 2 doses of every third day SQ dosing as defined in the protocol, another subject may be enrolled. 
With:
 
Replacement of a subject occurs for the following reason:
 
If a subject does not complete 21 days of daily SC dosing, as defined in the protocol, another subject may be enrolled.
8.1.1 Study Procedures: Screening	Additions	
PK: FIX activity
 
FIX genotype test

8.1.2 Study Procedures: Screening	Updated	
Part 1; Weeks 1 and 2 (Duration 7 days)
 
With:
 
Treatment (Duration 28 days)

8.1.2.1 Study Procedures: Day 1 Pre-dose evaluations	Updated	
Study Subject training on drug administration and injection site assessment

Dalcinonacog alfa_DLZ-201 VERSION 2.0, Amendment 1

		
With:
 
Study Subject training on diary entry, drug administration, adverse events and injection site assessment

8.1.2.1 Study Procedures: Day 1 Pre-dose evaluations	Deletion	
Review of diary entry of investigational drug administration, injection site assessment, adverse events, bleeding episodes & treatment

8.1.2.1 Administration	Update	
CB2679d administration (Every day from Day 1 to Day 14)
 
Subjects will receive a loading IV dose of 70 IU/kg, followed 35 ± 5 minutes later with a 140 IU/kg SQ dose of CB2679dSubjects will then administer a 140 IU/kg daily SQ dose of CB2679dSQ CB2679d should be self-administered by subjects at approximately the same time every day. 
With:
 
CB2679d administration (Daily from Day 1 to Day 28)
 
Subjects will receive a loading IV dose of 50 IU/kg, followed 35 ± 5 minutes later with a 100 IU/kg SC dose of CB2679dSubjects will then administer a 100 IU/kg daily SC dose of CB2679d from Day 2 until Day 28Daily SC dosing of CB2679d should be self-administered by subjects at approximately the same time every day.
8.1.2.4 Day 2 and 3 Pre-SC dose	Addition	
Hematology and chemistry – platelet count only (see Footnote 4 and 5 in Section 1.3, SOA)

Dalcinonacog alfa_DLZ-201 VERSION 2.0, Amendment 1

8.1.2.4 Day 2 and 3 Pre-SC dose evaluations	Updated	
Day 1 Post-SQ dose (Hour 7) and Day 2 Post-SQ dose (Hour 24) evaluations
 
Blood will be collected at hour 7 post-dose on Day 1 and hour 24 post-dose on Day 2 for the following evaluations:
 
• Thrombogenicity markers: Fibrinogen, D-dimer, F1+2, and TAT• PK: CB2679d activity 
Other evaluations will include:
 
• Concomitant medications• Vital sign• Physical examination• Clinical signs of thrombosis (see Appendix A)• Review of diary entry of investigational drug administration, injection site assessment, adverse events, bleeding episodes & treatment• Adverse events (from Hr 6 to 24 hours) 
With:
 
Day 2 and 3 Pre-SC dose evaluations
 
Blood will be collected pre-dose on Day 2 for the following evaluations:
 
• Hematology and chemistry – platelet count only (see Footnote 4 and 5 in Section 1.3, SOA): Day 2 ONLY• Thrombogenicity markers: Fibrinogen, D-dimer, F1+2, and TAT• PK: FIX activity 
Other evaluations will include:
 
• Concomitant medications
---	---------	--

Dalcinonacog alfa_DLZ-201 VERSION 2.0, Amendment 1

		
• Vital sign• Physical examination• Clinical signs of thrombosis (see Appendix A)• Review of diary entry of investigational drug administration, injection site assessment, adverse events, bleeding episodes & treatment• Adverse events
8.1.2.5 Day 7, 14, 21 and 28 Pre-dose evaluations	Updated	8.1.2.5 Day 5, 8, 11 and 14 Pre-dose evaluations With: 8.1.2.5 Day 7, 14, 21, and 28 Pre-dose evaluations
8 Study Assessments	Deletion of Selections	8.1.3 Part 2, Week 3 (Duration: 7 days) 8.1.3.1 CB2679d administration (Day 15, Day 17, Day 19, and Day 21) 8.1.3.2 Day 15 Pre-dose evaluations 8.1.3.3 Day 15 Post-dose (Hour 7), Day 16 Post-dose (Hour 24), Day 17 and Day 19 Pre-dose evaluations 8.1.3.4 Day 21 Pre-dose evaluations 8.1.4 Part 3, Weeks 4 and 5 (Duration: 14 days) 8.1.4.1 CB2679d administration (Day 23, Day 26, Day 29, and Day 32) 8.1.4.2 Day 23 and Day 32 Pre-dose evaluations 8.1.4.3 Day 23 Post-dose evaluations (Hour 7) 8.1.4.4 Day 24 Post-dose (Hour 24) and Day 26 and Day 29 Pre-dose evaluations

Dalcinonacog alfa_DLZ-201 VERSION 2.0, Amendment 1

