Treatment of a bleeding episode: Subjects will self-administer their currently prescribed FIX replacement product for treatment of any spontaneous or traumatic bleed that occurs while on study drug. If treatment for a breakthrough spontaneous bleeding episode is needed, then subjects will contact the clinical investigative team immediately to report the event; treatment dose administered; and arrange for an urgent follow-up visit to the study site for additional evaluation and laboratory testing, if needed.

Dose interruption: SQ study drug injections will be interrupted if any of the following occurs: a thrombotic event; clinical evidence of inhibitor formation; or laboratory results suggesting a high titer antibody may be developing; trough activity levels >80% or peak

CB2679d DLZ-201 VERSION 1.0

levels >175%, where subsequent dosing will be determined in consultation with the sponsor.

Surgery: If there is an urgent need for a surgical procedure or an event requiring extended (>48 hours) hospitalization, a FIX activity level will be urgently obtained and measured prior to the event, and the PI will confer with the Sponsor Medical representative regarding the need for any additional treatment and whether study drug requires interruption.

Measurements:

PK, PD, and safety assessments: CB2679d activity levels, as well as fibrinogen, D-dimer, prothrombin fragment 1+2 (F1+2), and thrombin-antithrombin complexes (TAT). PT and aPTT will be measured at screening and end of study visit only.

Immunogenicity assays: Specimens for immunogenicity testing (antibody to CB 2679d, wild-type FIX cross reactivity, and neutralizing activity) will be drawn at screening, on days 1, 8, 15, 23, 32, and end of study.

If the FIX activity level decreases unexpectedly by more than 25%, ie, IU/dL, as measured by the central or local lab, CB2679d activity levels will be drawn for analysis within 24 hours and immediately sent to the central laboratory. Specimens for fibrinogen, D-dimer, F1+2, and TAT and immunogenicity testing will also be drawn.

Number of planned subjects: 5

Trial population:

Inclusion criteria:

1. Confirmed diagnosis of severe (<2%) congenital hemophilia B.
2. Male, age 18 or older.
3. Agreement to use highly effective birth control throughout the study.

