Subjects will sign an ICF at the Screening Visit, prior to any study procedures.

Eligibility to participate in the study will be determined by inclusion and exclusion criteria from medical history, hemophilia history, laboratory investigations and ECG. The screening period duration may be up to 4 weeks.

At enrollment, subjects will receive training and diary entry of self-administered investigational drug administration & injection site assessment, bleeding episodes & treatment, evaluation & entry of AEs.

Treatment of a spontaneous or traumatic bleeding episode: Subjects will use their current prescribed treatment regimen for any spontaneous or traumatic bleed that occurs while on study drug. If treatment for a spontaneous or traumatic bleeding episode is needed, then subjects will contact the clinical investigative team immediately to report the event, treatment dose administered, and determine follow-up plans for that event including whether to arrange for a blood specimen to be drawn (if feasible) before further administration of either study drug or the current prescribed treatment regimen used. Decision whether to continue daily study drug administration will also be determined by the clinical study team after discussion with the Sponsor.

Dose interruption: SQ study drug injections will be interrupted if any of the following occurs: a thrombotic event; clinical evidence of inhibitor formation; or laboratory results suggesting a high titer antibody may be developing; trough activity levels $>80\%$ or peak levels $>175\%$ where subsequent dosing will be determined in consultation with the sponsor.

Surgery: If there is an urgent need for a surgical procedure or an event requiring extended (>48 hours) hospitalization, a FIX activity level will be urgently obtained and measured prior to the event, and the PI will confer with the Sponsor Medical representative regarding the need for any additional treatment and whether study drug requires interruption.

CB2679d DLZ-201 VERSION 1.0

Measurements:

PK, PD, and safety assessments: CB2679d activity levels, as well as fibrinogen, D-dimer, F1+2, and TAT. PT and aPTT will be measured at screening and end of study visit only.

Immunogenicity assays: Specimens for immunogenicity testing (antibody to CB 2679d, wild-type FIX cross reactivity, and neutralizing activity) will be drawn at screening, pre-dose on days 1, 8, 15, 23, 32 and end of study.

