investigative team immediately to report the event, treatment dose administered, and determine follow-up plans for that event including whether to arrange for a blood specimen to be drawn (if feasible) before further administration of either study drug or the current prescribed treatment regimen used. Decision whether to continue daily study drug administration will also be determined by the clinical study team after discussion with the Sponsor.

Dose interruption: SC study drug injections will be interrupted if any of the following occurs: a thrombotic event; clinical evidence of inhibitor formation; or laboratory results suggesting a high titer antibody may be developing; trough activity levels >80% where subsequent dosing will be determined in consultation with the sponsor.

Surgery: If there is an urgent need for a surgical procedure or an event requiring extended (>48 hours) hospitalization, a FIX activity level will be urgently obtained and measured prior to the event, and the PI will confer with the Sponsor Medical representative regarding the need for any additional treatment and whether study drug requires interruption.

Measurements:

PK, PD, and safety assessments: FIX activity levels, as well as fibrinogen, D-dimer, F1+2, and TAT. PT and aPTT will be measured at screening and end of study visit only. Genotype testing will be performed at screening.

Immunogenicity assays: Specimens for immunogenicity testing (antibody to CB2679d, BeneFIX®, and neutralizing activity) will be drawn at screening, pre-dose on days 7, 14, 21, 28 and end of study.

If the FIX activity level decreases unexpectedly by more than 25%, ie, IU/dL, as measured by the central or local lab, FIX activity levels will be drawn for analysis within 24 hours and immediately sent to the central laboratory. Specimens for fibrinogen, D-dimer, F1+2, and TAT and immunogenicity testing will also be drawn.

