6.2. Key Definitions

6.2.1. Baseline and Change from Baseline

Baseline is defined as the last assessment (pre-dose) before the first administration of study drug.

Change from baseline = (post-baseline value – baseline value).

Maximum absolute change from baseline will be calculated as the maximum of the absolute changes from baseline over all visits during treatment period.

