11.7. Physical Examination

All physical examination data will be listed by subject and time of measurements.

11.8. Occurrence of a confirmed antibody response to CB2679d and whether it is inhibitory and cross-reactive to BeneFIX.

Antibody response and neutralizing antibodies will be measured. The schedule of assessments of immunogenicity will be defined as follows: Screening, pre-dose on Day 7, Day 14, Day 21, Day 28, and EOS.

Following endpoints will be analyzed: occurrence of antibody response to CB2679d, BeneFIX and neutralizing activity to CB2679d and BeneFIX for the Safety Population.

The sampling for immunogenicity results will be listed combining all time points and confirmation assay in binary form (Positive/Negative) with the value of titer for positive immune response.

The immunogenicity results will be summarized by frequency of anti-drug antibody (ADA) positive subjects at each time point for the Safety Population.

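### No antibody sample is taken on Day 1 before the first dose, so an antibody change first seen on Day 7 cannot be placed before or after study drug began

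*Protocol*

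**What the plan says.** Protocol v2.0 section 4.1 states that immunogenicity specimens "will be drawn at screening, pre-dose on days 7, 14, 21, 28 and end of study". For the synopsis, the Amendment 1 summary of changes gives the new text as specimens that "will be drawn at screening, on days 7, 14, 21, 28, and end of study". The v2.0 synopsis (1.1) gives the same days, and the Schedule of Activities (1.3) has no immunogenicity mark under Day 1. Section 8.1.2.1, the Day 1 pre-dose list, includes hematology, chemistry, thrombogenicity markers and FIX activity but no antibody assay. v2.0 Appendix B also omits it for Day 1.

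SAP 11.8 repeats the schedule: "Screening, pre-dose on Day 7, Day 14, Day 21, Day 28, and EOS". It lists each result as positive or negative, with titers for positives, and summarizes the frequency of antibody-positive subjects at each time point. SAP 6.2.1 says: "Baseline is defined as the last assessment (pre-dose) before the first administration of study drug". Applied to antibodies, that is the screening sample.

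Screening runs from Day -28 to Day -1 (v2.0 section 1.3) and includes antibody to both CB2679d and BeneFIX (section 8.1.1). Exclusion 2 (section 5.2) removes subjects with a positive FIX antibody at screening.

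Protocol v1.0 was inconsistent about a Day 1 sample. Its synopsis said specimens "will be drawn at screening, on days 1, 8, 15, 23, 32, and end of study", its section 4.1 said "drawn at screening, pre-dose on days 1, 8, 15, 23, 32 and end of study", and its Appendix B entry for Day 1 before the IV dose listed "coagulation assay, thrombogenicity markers, PK sampling, immunogenicity assays". Its Schedule of Activities and its section 8.1.2.1 had no Day 1 antibody sample.

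**The concern.** Antibody response to CB2679d is a secondary endpoint (Protocol 9.1, SAP 4.2), and an immune response with antibody formation is an adverse event of special interest (Protocol 8.4.7). It is a live question for this product. Of the two earlier subjects given IV plus SC dosing in cohort 6, the amendment's summary of changes reports: "Neutralizing antibodies developed in both subjects, (transiently in one subject".

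A reader of the results will want to know whether an antibody arose after exposure in this study. That needs a sample close to the first dose. Here the last drug-free sample may be four weeks old, and the subject's own FIX product may be used in between, since section 6.5 sets no concomitant medication restrictions. The next sample is on Day 7 (± 1 day), after several daily doses.

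The SAP also gives no rule for calling an antibody treatment-emergent, although SAP 11.3 does so for adverse events by reference to the first dose.

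**Working it through.** The plan states no figure on this point, and Protocol 9.2 says that no formal sample size calculation was needed. There is nothing to reproduce. The check is a count of days.

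Inputs:
- Screening sample: Day -28 to Day -1 (v2.0 section 1.3).
- First dose: Day 1. I assume there is no Day 0, so Day -a to Day 1 is a days.
- First on-treatment antibody sample: Day 7 ± 1, that is Day 6, 7 or 8 (v2.0 section 1.3).
- Planned subjects: 6 (v2.0 section 9.2).

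Formulas, for screening on Day -a and sampling on Day d:
- days before drug = a
- days on drug = d − 1
- share before drug = a / (a + d − 1)

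| Screening | Sample | Before drug | On drug | Total | Share before drug |
|---|---|---|---|---|---|
| Day -28 | Day 6 | 28 | 5 | 33 | 28/33 = 84.8% |
| Day -28 | Day 7 | 28 | 6 | 34 | 28/34 = 82.4% |
| Day -28 | Day 8 | 28 | 7 | 35 | 28/35 = 80.0% |
| Day -14 | Day 7 | 14 | 6 | 20 | 14/20 = 70.0% |
| Day -1 | Day 6 | 1 | 5 | 6 | 1/6 = 16.7% |
| Day -1 | Day 7 | 1 | 6 | 7 | 1/7 = 14.3% |
| Day -1 | Day 8 | 1 | 7 | 8 | 1/8 = 12.5% |

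With a Day 1 pre-IV sample, the unobserved time before drug falls from 1–28 days to 0. The interval up to the Day 7 sample becomes 5 to 7 days, all on study drug.

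Which results are ambiguous:
1. Positive at screening, titer not higher on Day 7: seen before any study drug. Not ambiguous.
2. Negative at screening, positive on Day 7: ambiguous.
3. Positive at screening, higher titer on Day 7: the rise can be shown but not dated relative to the first dose. Ambiguous.
4. Negative at screening and on Day 7, positive on Day 14 or later: the last negative sample was taken on drug. Not ambiguous.

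For scale, if a treatment-emergent proportion were reported, each of six subjects would carry 1/6 = 16.7 percentage points. The per-visit count that SAP 11.8 now plans would not change, because it counts a Day 7 positive whatever its origin.

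**The case against.** The strongest reply is that a pre-treatment antibody baseline already exists. Screening tests antibody to both products, and v2.0 section 4.1 adds neutralizing activity. Subjects with a FIX antibody at screening, or with a personal or family history of inhibitors, are excluded. Parallel CB2679d and BeneFIX results help to separate product-specific reactivity from reactivity to the subject's own FIX. FIX activity before the IV dose, 35 minutes after it, and on Days 2 and 3 gives a functional view around first exposure. An unexpected fall of more than 25% triggers immunogenicity testing. All of this stands and narrows the gap, but none of it dates a conversion that falls between screening and Day 7.

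Several stronger readings are tempting, and the documents do not support them:
- A reader might infer that no Day 7 antibody can be told apart from a pre-existing one. That fails, because an antibody detectable at screening is seen there.
- A reader might take 82% as typical, or as a probability. It is the extreme of the screening window and a share of calendar days.
- A reader might say that antibody to CB2679d is not an exclusion. Exclusion 2 refers to antibody to FIX, and CB2679d is a FIX variant; the text does not settle the matter.
- A reader might cite the cohort 6 root-cause analysis as showing that antibody timing was the issue. Section 2.2.2 attributes those antibodies to a 3-month gap between two dosing periods and says nothing about a missing pre-dose sample.
- A reader might say that Amendment 1 simply dropped a planned sample. v1.0 contradicted itself, so the amendment also removed an inconsistency, and a difference from superseded text is not itself an error. The point rests on the current text.

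**Conclusion.** The point holds in a limited form and is minor. The current plan has no antibody sample on the day of first dose, and the antibody baseline is 1 to 28 days old. A conversion or titer rise first seen on Day 7 cannot be placed before or after the first dose. The interval in doubt runs from 7 days (14% before drug) to 34 days (82% before drug) at the nominal Day 7 visit, or 6 to 35 days with the visit window. SAP 11.8 does not separate pre-existing from treatment-emergent antibody.

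This assumes that there is no Day 0, that the screening antibody sample may fall anywhere in the window, and that the Day 7 sample is taken; if it is missed, the same doubt passes to the next sample. The documents give no probability of conversion during screening, and it is probably small. The case for change is that the lost information cannot be recovered later and costs little to secure.

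**What to change.** Add one immunogenicity aliquot to the existing Day 1 pre-IV draw, in the Schedule of Activities, Protocol 4.1 and 8.1.2.1, and SAP 11.8, and name it the antibody baseline. It may be stored and assayed only if a later sample is positive.

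In SAP 11.8, define treatment-emergent antibody as negative on Day 1 and confirmed positive later. For subjects positive on Day 1, list any titer rise over the Day 1 value.

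If Day 1 samples were not taken, define the same rule against the screening sample and report each subject's screening-to-Day 1 interval beside any Day 7 positive.

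The cost is six aliquots from a venipuncture already scheduled, at most six extra assays, and a short amendment. The fallback needs only SAP text and one listing column.
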